In this way, all participants will remain in the study for at least the first 7 days and will be included in the analysis on the effects of KD on withdrawal symptoms, benzodiazepine use, MRI and NPT within the first 7 days. After 7 days participants may be withdrawn from the study based on non-compliance to the diet.

4. **MRI scans:** MRI evaluations of the brain are being performed at 3Tesla (3T) (Siemens Prisma). These MRI scans are performed on FDA-approved scanners with approved radiofrequency coils, and their use conforms to the corresponding FDA labels. The MR scanner is being used in normal mode (not research mode) using the following pulse sequences: magnetization-prepared rapid gradient-echo (MPRAGE), Prospective Acquisition Correction (3D PACE), diffusion tensor imaging (DTI), echo-planar imaging (EPI), arterial spin-labeling (3D ASL), and Magnetic Resonance Spectroscopy (MRS).

MR acquisition: A high resolution T1-weighted magnetization-prepared rapid gradient-echo pulse sequence (MP2RAGE) will be used to map brain structure with high spatial resolution and excellent gray-white contrast and to map T1 relaxation in the brain. DTI, an MRI technique that can quantify isotropic and anisotropic water diffusion, will be used to map fractional anisotropy and the apparent diffusion coefficient, and to assess the structural connectivity of the brain. ASL, an MRI-based method that utilizes blood as an endogenous tracer and provides noninvasive quantification of tissue perfusion, will be used to map CBF in the resting state. BOLD-weighted functional images will be collected to measure brain activation and to map functional connectivity. *Brain activation paradigms:* We will use passive viewing of neutral, food and drug related pictures [40 pictures per category; the neutral, alcohol and food pictures will be selected from freely available online and in-house collections) [71, 72]. Pictures will also be rated for characteristics such as valence, liking and wanting. The stimuli are presented to the subjects on an MRI-compatible 32-inches LCD screen synchronized with the MR acquisition using an MRI trigger pulse.

We will use the delayed discounting task (DDT) to evaluate effects on self-regulation. The DDT task has been used extensively [for review see [73]. It

allows measurement of BOLD response to immediate reward responses versus responses to delayed rewards.

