Empirical knowledge regarding the necessary sample size for significant effects of a ketogenic diet on withdrawal, NP or brain functioning in AUD during withdrawal does not exist. Previous behavioral and pharmacological treatment studies in AUD with behavioral, fMRI and MRS as outcome measures have studied on average 20-25 patients per group [treatment versus control: reviewed in 109]. Clinical efficacy of a ketogenic diet in epilepsy was established in randomized-controlled trials in 20 [55] or 94 epilepsy patients [56]. In 20 elderly participants, an acute dose of ketogenic meal improved executive functioning 1.5-3 hours after, as compared to a control meal on a different day [58]. Further, beneficial effects of KD on sleep was established in a study in 18 children with epilepsy [57]. Thus, for within-subject fMRI studies in individuals with AUD sample sizes of 25 patients per group have been effective for obtaining interpretable data regarding behavioral and neurocognitive effects of treatment, suggesting that the sample size of the current protocol is adequate for the identification of effects of ketogenic diet in AUD.

Independent sample t-test will be used to test **Hypothesis 1**, “withdrawal symptom severity within the first week of detoxification will be lower for patients with KD compared to control diet”.

Paired t-test on BOLD signals will be used to test **Hypothesis 2**, “limbic activation to alcohol cues would be reduced after 3 weeks of treatment”; **Hypothesis 3**, “the functional connectivity of the saliency network will be stronger after 3 weeks of treatment”; **Hypothesis 4**, ‘prefrontal cortex atrophy and ventricular enlargement will stronger decrease after 3 weeks of KD treatment compared to control diet’. Assuming a threshold probability for rejecting the null hypothesis (Type I error rate), $\alpha = 0.05$, and a probability of failing to reject the null hypothesis under the alternative hypothesis (Type II error rate), $\beta = 0.2$, the

proposed sample sizes (25 KD versus 25 ND) will allow us to detect an effect size of 0.66.

To test KD treatment effects, mixed ANOVAs will be used to assess whether KD group shows reduced brain activation (Hypothesis 2), higher functional connectivity (Hypothesis 3), and prefrontal cortex atrophy and ventricular enlargement (Hypothesis 4) compared to the control diet group. Assuming $\alpha = 0.05$ and $\beta = 0.2$, the proposed sample sizes will allow us to detect an effect size of 0.9.

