Pearson correlation will be used to test **Hypothesis 5**, “acetone and β -hydroxybutyrate concentration in the anterior cingulate and frontal white matter will increase linearly as a function of time week #1, #2 and #3”. Assuming $\alpha = 0.05$ and $\beta = 0.2$, the proposed sample sizes will allow us to detect statistically significant correlation coefficients, $r > 0.6$.

From our past experience with neuroimaging of patients with AUD, it is expected that, even with careful screening and preparation, approximately 50% of participants will not be able to complete protocols with neuroimaging like the current one being proposed. Thus, we are proposing to recruit 100 participants in order to complete studies in 50 of them (25 on KD and 25 on SA diet).

* We expect that more than 25 patients per group will finish the first week of KD and its assessment of withdrawal symptoms, and will therefore include all patients who finished these assessments to test Hypothesis 1.

11. Human Subjects Protection

a. Subject selection

Adults who fulfill the eligibility criteria will be included, regardless of race, ethnicity, sex, or religious affiliation. We predict the racial composition is approximately 60% Caucasian, 35% African American, and remaining 5% proportion of Asian or other. We predict the Hispanic ethnicity to be approximately 25%. On the same basis, the expected breakdown is 70% male and 30% female. The age range of 18 years and older will provide a sample size that hits our target inclusion criteria of a minimum of 5 year of heavy drinking history.

b. Justification for exclusion of children

Children are excluded since it is unlikely that they will meet the ten-year criteria of heavy drinking required for the study.

c. Justification for exclusion of other vulnerable subjects

Vulnerable populations such as those who lack capacity to consent, are also excluded due to the likely inability to follow instructions for tasks to be performed during diet (KD or SA meal/shake protocol) randomization, MR scans and NP

testing. We also exclude individuals with major psychiatric disorders since this may affect brain function and structure, and may influence study results.

d. Justification for sensitive procedures

N/A

e. Safeguards for vulnerable populations and sensitive procedures

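### The detectable effects in section 10.b (0.66, 0.9, r > 0.6) do not follow from 25 per group at the stated error rates, Hypothesis 4 is listed under a test that cannot address it, and the Pearson test for Hypothesis 5 ignores repeated measurement

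*Combined protocol and SAP*

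**What the plan says.** All of the following is in section 10.b (Power analysis) unless another place is named.

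- For Hypotheses 2 to 4: "Paired t-test on BOLD signals will be used to test" them. At alpha 0.05 and beta 0.2, the "proposed sample sizes (25 KD versus 25 ND) will allow us to detect an effect size of 0.66".
- Hypothesis 4, in that same list, reads: "prefrontal cortex atrophy and ventricular enlargement will stronger decrease after 3 weeks of KD treatment compared to control diet".
- The next paragraph changes the test: "To test KD treatment effects, mixed ANOVAs will be used to assess whether KD group shows reduced brain activation (Hypothesis 2"), and it goes on to name Hypotheses 3 and 4. At the same alpha and beta, "the proposed sample sizes will allow us to detect an effect size of 0.9".
- Hypothesis 5 holds that brain acetone and β-hydroxybutyrate "will increase linearly as a function of time week #1, #2 and #3". The test is a Pearson correlation, and "the proposed sample sizes will allow us to detect statistically significant correlation coefficients" above 0.6.
- Section 4.e, item 4 (MRI scans) says which sequence images structure: a T1-weighted "pulse sequence (MP2RAGE) will be used to map brain structure with high spatial resolution".
- Section 4.a has the scans repeated weekly in the same patients.

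Section 10.b does not state sidedness, the effect-size metric, a within-patient correlation, which arm or arms enter the paired and Pearson tests, or how many visits enter the mixed ANOVA.

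**The concern.** A detectable effect quoted with alpha, beta and n should be reproducible from those three inputs. None of these three figures is, in its usual metric, one-sided or two-sided.

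Two of the named tests also do not fit their hypotheses. A paired test compares a patient with himself or herself, so it cannot compare diets, and a BOLD signal does not measure cortical or ventricular volume. A Pearson test assumes independent points, whereas three weekly scans of one patient are repeated measurements.

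Spectroscopy and structural MRI are among the primary objectives (section 2.a) and primary outcome measures (section 9.a), so their tests should be unambiguous. The stakes are still limited: the sample size is argued mainly from precedent, and nothing here changes recruitment.

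**Working it through.** **Inputs (section 10.b).** Alpha 0.05; power 0.80; 25 completers per group. Sidedness is not stated, so both are tried.

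**Formulas.** With z(0.975) + z(0.80) = 1.960 + 0.842 = 2.802, the normal approximations are:
- paired: 2.802/√n; for n = 25, 2.802/5 = 0.560;
- two groups: 2.802 × √(2/n); for n = 25 each, 0.792;
- correlation (Fisher z): tanh(2.802/√(n − 3)); for n = 25, tanh(0.597) = 0.535.

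The table uses the noncentral t for the first two. An exact calculation for r at n = 25 gives 0.526.

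| Setting | Paired | Between diets | r |
|---|---|---|---|
| Stated in 10.b | 0.66 | 0.9 | > 0.6 |
| n = 20, two-sided | 0.660 | 0.909 | 0.591 |
| n = 25, two-sided | 0.584 | 0.809 | 0.535 |
| n = 25, one-sided | 0.512 | 0.713 | 0.485 |
| n = 25, alpha 0.025 two-sided | 0.651 | 0.896 | 0.577 |

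The paired value for both arms pooled (n = 50, two-sided) is 0.404. The between-diet value of 0.809 is for a two-visit change score; a three-visit interaction is a different test.

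**Raw-SD reading.** If the effect is expressed in single-visit SDs, multiply by √(2(1 − ρ)), where ρ is the within-patient correlation. The documents give no ρ, so a range is shown for 25 per group.

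| Assumed ρ | Paired | Between diets |
|---|---|---|
| 0.3 | 0.69 | 0.96 |
| 0.37 | 0.66 | 0.91 |
| 0.5 | 0.58 | 0.81 |
| 0.7 | 0.45 | 0.63 |

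A ρ near 0.37 recovers 0.66 and 0.9, but it has no bearing on r > 0.6.

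**Power at the stated figures** (25 per group, two-sided, SD of change): paired 0.66, 88.6%; between-diet 0.9, 87.7%; r = 0.6 on 25 independent pairs, about 90%. A between-diet effect of 0.66 has 62.8%.

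**Hypothesis 5 with the weeks pooled.** Code time as −1, 0, 1 and let the patient-intercept, patient-slope and residual variances be a, s and e. With n patients:
- true variance of the fitted slope: (s + e/2)/n;
- variance that Pearson assumes: (a + e + 2s/3)/(2n).

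The first exceeds the second when s > 0.75a. Pearson is therefore too conservative when patients differ mainly in level, and too liberal when their slopes differ enough. Simulation with 25 patients and three weeks, nominal two-sided 5%, under assumed variances:

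| a / s / e | Pearson error under no trend |
|---|---|
| 0 / 0 / 1 | 5.1% |
| 0.3 / 0 / 0.7 | 2.1% |
| 0.5 / 0 / 0.5 | 0.8% |
| 0.7 / 0 / 0.3 | 0.06% |
| 0.3 / 0.2 / 0.5 | 4.7% |
| 0.3 / 0.4 / 0.3 | 8.1% |
| 0.1 / 0.5 / 0.4 | 12.7% |

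A one-sample t-test on patient slopes stays close to 5% in every row. With no slope variation and an assumed rise of 0.3 SD per week, power for Pearson against the slope test is 56% v 53% (a = 0), 57% v 69% (0.3), 58% v 82% (0.5) and 60% v 96% (0.7).

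**The case against.** **The figures are attainable.** The trial can detect 0.66, 0.9 and r = 0.6, with 88% to 90% power rather than 80%. That is true, and it is why the discrepancy is harmless in direction. But an effect quoted beside beta = 0.2 is read as the effect detectable with 80% power, and on that reading the numbers do not follow.

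**The metric was never stated.** A raw-SD metric with ρ near 0.37 gives two of the three figures, and alpha 0.025 comes near all three. Neither is in the text, and the stated alpha is 0.05. What stands is that the figures cannot be called impossible, only unverifiable from the plan's own inputs. Likewise, a reader might infer that they were carried over from a calculation for 20 per group. The match is close, but no document says so.

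**Hypothesis 4 already has a suitable test.** The mixed ANOVA covers it, and section 10.a describes separate structural processing. A reader might conclude that the structural diet contrast has no valid analysis; the documents do not support that. The fault is the duplicate listing and the 0.66 beside it. The 63% power arises only if 0.66 is applied to a diet contrast.

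**Pooling is not stated for Hypothesis 5.** That is correct, so the error-rate results are conditional. It is also tempting to say that pooled Pearson is simply over-conservative. That holds when patients differ only in level; the documents give no variance components, and slope variation can reverse it.

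**Conclusion.** The point holds as a minor one about reporting and specification.

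- **Figures.** At 25 per group, two-sided and in SD-of-change units, the stated inputs give 0.58 (one arm) or 0.40 (both arms pooled), 0.81 (two-visit diet contrast) and r of about 0.53 to 0.54, against 0.66, 0.9 and r > 0.6. A reader might infer an underpowered trial. The documents do not support this: against these metrics the stated figures understate sensitivity.
- **Hypothesis 4.** It carries two tests and two detectable effects, and one of those tests cannot address it.
- **Hypothesis 5.** The Pearson test does not suit a within-patient trend. If the weeks are pooled, its true error in the illustrations runs from well under 1% to about 13%, depending on variances that the documents do not give.

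The arithmetic is certain given the metric. The size of the Hypothesis 5 problem rests on assumed variances and on pooling.

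**What to change.** 1. For each test in section 10.b, state sidedness, effect-size metric, arm or arms, n and number of visits.
2. Restate the detectable effects for 25 completers per group, two-sided, in SD-of-change units: 0.58 for a paired test in one arm, or 0.40 if both arms are pooled, and 0.81 for a two-visit change contrast between diets. Alternatively, keep 0.66 and 0.9 and state the raw-SD metric and the within-patient correlation (about 0.37) that yield them.
3. Delete Hypothesis 4 from the paired t-test sentence and leave it under the mixed ANOVA.
4. For Hypothesis 5, replace the Pearson test and r > 0.6 with a one-sample t-test on each patient's slope over weeks 1 to 3, or a mixed model with a random intercept and slope per patient. With 25 patients, the slope test has 80% power for a mean slope of 0.58 SD of the patient slopes.

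The cost is rewording three paragraphs and changing one planned test on data already being collected. Recruitment, visits and procedures stay as they are.

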8. Presence of ferromagnetic objects in the body that are contraindicated for MRI of the head, fear of enclosed spaces, or other standard contraindication to MRI (self-report checklist).
9. Cannot lie comfortably flat on his/her back for up to 2 hours in the MRI scanner (self-report).
10. Body weight > 550 lbs. The MR scanner bed is tested to a weight limit of 550 lbs.
11. Milk or soy allergy (self-report).

Note that subjects will not be excluded on initial screening from enrollment onto this study if their breath alcohol test is positive; or if their urine test is positive for drugs. The following guideline will be followed for positive alcohol/drug screens on study procedure days:

- If an AUD subject's breath alcohol and/or urine drug screen test is/are positive on study days (i.e., within 24 hours before study procedures except for benzodiazepines during detox, including oxazepam [™Serax]), the procedures will be postponed and rescheduled to another day. If the urine drug screen is positive for THC-COOH, a saliva drug screen will be performed and subject may proceed with MRI/NPT procedures if saliva results for THC are negative. We will not place a limit on rescheduling study days.

4. Study Design and Methods

a. Study overview

This study includes an inpatient component and outpatient follow-up.

Patients are admitted to the Clinical Center (CC) for detoxification and treatment as usual (TAU) under protocol 14-AA-0181. Under the current protocol, patients will be randomized into a meal and shake plan consisting of either a standard American (SA) versus a ketogenic diet (KD). Patients will be given benzodiazepines only if withdrawal symptoms emerge while receiving either the KD or the SA diet. Subjects may be administered benzodiazepines only if withdrawal symptoms emerge. On day 2-6 after admission, all patients will undergo an MRI (brain structure, functional reactivity, functional connectivity and MRS) and will have a battery of neuropsychological tests (NP). Personality tests will be obtained during week 1 at the time of NP testing. The MRI scans will be repeated at 1 week intervals (Week 2 and 3). The Sleep Profiler device will be obtained 2X p/week in weeks 1-3. The ™GENEActiv (actigraphy) will be done for an entire week in weeks 1 and 3. The NP studies will be repeated coincident with the last MRI session. We will complete studies on at least 25 alcoholics with the ketogenic diet and 25 with the regular diet.

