age will be used to determine how many calories are provided to each participant. While on the KD/SA diet, patients are limited to drink non-caloric drinks (water, diet soda, coffee and tea without milk or sugar). In addition to the diets, MRI/fMRI/MRS scans, genetic tests, self-report ratings, motor activity, sleeping behavior, NP testing and personality measures will be obtained in all participants. The first MRI session and the first NP testing will be performed within the first 2-6 days of admission. The MRI sessions will be repeated on a weekly basis (second and third week of hospitalization; the later corresponding to the last week of their inpatient stay) and the NP testing will be repeated during the third week of hospitalization. MRI scanning session and NP tests are described below and are for research purpose only.

During the inpatient period, participants will be periodically monitored for signs of withdrawal and evaluated for mood, sleep and alcohol cravings. Compliance with diet adherence (KD or SA) will be closely monitored during the hospital stay using daily urine tests.

After the final MRI sessions, the study diets are discontinued and the individual blind will be broken on a per subject basis. If KD is discontinued this will be done by slowly increasing the levels of carbohydrates to the diets of the SA group [68]. The levels of carbohydrates in the control group remains constant throughout the study, but patients are still blind to treatment group.

Participants will then be released at about 3-4 weeks from the Clinical Center and will have a 3 month follow up period under this protocol which is discussed below in section 4.d.12 *Follow-Up*.

1. Ketogenic Diet (KD) / Standard American (SA) Snacks and Shakes: Participants will be randomized to a meal plan of either a ketogenic diet (KD) or standard American (SA) diet at the time they sign the consent (day 1 or 2 of admission). For each meal at breakfast, lunch and dinner, the diets will consist of SA meal (carbohydrate rich) or KD meal depending on treatment randomization. Compliance tests are done daily with urine tests measuring ketone levels by an independent person (BSN RN) [69], results of which are retained. To ensure that the diet is double blind in both the outpatient and inpatient phases, solid snacks are always ketogenic and shakes are either KD or SA.

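### The mixed ANOVA for Hypotheses 2–4 has no missing-data rule and cannot use patients without a week-3 scan; a likelihood-based mixed model would give a modest gain in precision and some protection against unequal dropout

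*Combined protocol and SAP*

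**What the plan says.** Section 10.b (Power analysis) states that "mixed ANOVAs will be used to assess whether KD group shows reduced brain activation", and likewise for connectivity (Hypothesis 3) and for atrophy and ventricular size (Hypothesis 4). The power statement reads "Assuming $\alpha = 0.05$ and $\beta = 0.2$, the proposed sample sizes will allow us to detect an effect size of 0.9", and the paragraph before it gives the sample as 25 per diet. The section does not say which scan sessions enter the ANOVA, who is in the analysis set, or what happens when a session is missing. Section 10.a names software and model types but no missing-data method for these hypotheses.

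On attrition, 10.b expects that "approximately 50% of participants will not be able to complete protocols with neuroimaging", so 100 are recruited to complete 50. A note at the end of 10.b extends the analysis to all patients with the assessments, but for Hypothesis 1 only.

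There are three scan sessions (sections 4.a and 4.e): days 2–6, week 2 and week 3. Section 4.e, item 3 (Diet Compliance) says that "all participants will remain in the study for at least the first 7 days". The same sentence puts these patients in an analysis of diet effects within the first 7 days, and names MRI. Item 2 (Randomization and blinding) expects more dropout on KD. It sets a 3:2 ratio for the first 20 participants, to be reviewed afterwards. Item 3 also has a ketone-based removal rule that applies to the KD arm alone.

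**The concern.** The named test and the expected attrition do not fit together. A conventional mixed ANOVA needs a value at every modelled session. Hypotheses 2–4 are worded as effects after 3 weeks, so session 3 must be one of them. A patient who leaves after session 1 or 2 therefore falls out of the test, although the scans have been acquired.

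Two things are at stake. The first is precision in comparisons that rest on 25 per arm. The second is bias. Completers in the two arms may not be comparable if leaving is more common on KD and is related to the patient's condition. A completers-only analysis needs a stronger assumption about missing data than a likelihood-based one.

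**Working it through.** **1. The plan's own figure.** In a design with two groups and two sessions, the group-by-time test is a two-sample t-test on change. With 25 per group, two-sided alpha 0.05 and power 0.80, the detectable effect is 0.81 SD of change, not the stated 0.9. At 0.9 the power is 0.88. The stated figure corresponds to about 20 per group (0.91). That mismatch is conservative and is a separate matter. Below, the reference is power 0.80 at 0.81 (0.809 before rounding) with 25 completers per arm.

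**2. What is not in the documents.** Neither the number of partly scanned leavers nor the correlation between sessions is given. Assumed correlations: compound symmetry at 0.6 and 0.8, and AR(1) at 0.7 and 0.85 (session 1 to session 3: 0.7² = 0.49 and 0.85² = 0.72). Between 0 and 60% of leavers also have session 2.

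**3. Formula.** Take the single-scan variance as 1 and let ρ be the correlation of sessions 1 and 3. For one arm with n completers, the variance of the mean change is

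- completers only: 2(1 − ρ)/n
- with m further patients who have session 1 only: (1 − ρ²)/n + (1 − ρ)²/(n + m)

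Example with ρ = 0.6, n = 25, 17 KD and 8 SA leavers with session 1 only:

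- completers only, per arm: 0.8/25 = 0.0320; both arms 0.0640
- KD: 0.64/25 + 0.16/42 = 0.0256 + 0.0038 = 0.0294
- SA: 0.64/25 + 0.16/33 = 0.0256 + 0.0048 = 0.0304
- ratio R = (0.0294 + 0.0304)/0.0640 = 0.93

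With session-2 scans as well, each arm's information matrix is the sum over the observed patterns (sessions 1–3, 1–2, 1 only), and the variance is that of session 3 minus session 1. Effective completers per arm are 25/R. Power comes from the noncentral t with 48 degrees of freedom and noncentrality 0.809 × √12.5 / √R = 2.86/√R.

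| Scanned leavers (KD, SA) | R | Effective completers per arm | Power |
|---|---|---|---|
| 5, 5 | 0.93–0.98 | 25.4–26.8 | 0.81–0.83 |
| 12, 5 | 0.90–0.98 | 25.6–27.9 | 0.81–0.84 |
| 17, 8 | 0.86–0.97 | 25.8–29.0 | 0.81–0.86 |
| 35, 15 (upper bound) | 0.79–0.95 | 26.3–31.7 | 0.82–0.88 |

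The last row assumes 60 KD and 40 SA randomised, 25 completing in each, and every leaver scanned. These figures treat the covariance as known, so they flatter the mixed model slightly.

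**4. Bias.** Simulation of 8,000 trials per scenario: 50 patients per arm, no true diet effect, about half leaving, compound symmetry. Values are the mean error of the contrast in single-scan SDs.

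| Dropout | ρ | Completers only | Likelihood |
|---|---|---|---|
| Unrelated to outcome | 0.5 / 0.7 | 0.00 / 0.00 | 0.00 / 0.00 |
| Depends on week-1 value, both arms alike | 0.5 / 0.7 | 0.00 / 0.00 | 0.00 / 0.00 |
| Depends on week-1 value in KD only (logit slope 1) | 0.5 / 0.7 | 0.21 / 0.13 | 0.00 / 0.00 |

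The SD of change is √(2(1 − ρ)): 1.00 at ρ = 0.5 and 0.77 at ρ = 0.7. The bias is therefore 0.208/1.00 = 0.21 or 0.125/0.77 = 0.16 SD of change, which is about a quarter or a fifth of the detectable 0.81.

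**The case against.** The plan never states a complete-case rule. It is inferred from the method's name, from the sizing on completers, and from the all-assessed note being limited to Hypothesis 1. The ANOVA may use only weeks 1 and 3, in which case a completer who missed week 2 stays in and week-2 scans go unused for everyone. This stands, but under either reading a patient without session 3 drops out.

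A reader might infer that half the patients' scans are thrown away, or that a quarter to a third of all scans are wasted. The documents do not support that. Section 4.e gives first-week MRI of leavers a use in the first-7-day analysis. Section 3.a counts people who fail the eligibility criteria within the 50%, and they would never be scanned. The 3:2 ratio is fixed for 20 participants only. Unused shares of 50/200 (25%) to 80/230 (35%) arise only if all 50 non-completers were randomised and scanned.

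The precision gain is also not assured. Where dropout depended on the week-1 value alike in both arms, neither analysis was biased, and the likelihood estimate was slightly more variable (SD 0.300 against 0.283 at ρ = 0.5). That version used sessions 1 and 3 only.

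Finally, the baseline is unclear. Section 4.e says "The first MRI session and the first NP testing will be performed within the first 2-6 days of admission", while randomisation is at consent on day 1 or 2. Session 1 may therefore follow the start of the diet, and session 3 minus session 1 would remove any early diet effect. This stands and has to be stated with the contrast.

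**Conclusion.** The point holds in a limited form. The stated test for Hypotheses 2–4 has no missing-data rule, and a patient without a week-3 scan cannot contribute to it. Under the assumed 5–17 KD and 5–8 SA scanned leavers, the precision lost is modest: about 2–14% of the variance, or power of 0.80 instead of 0.81–0.86. The ceiling of 5–21% and 0.88 needs every non-completer to have been scanned.

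The stronger reason to change is bias. The plan itself expects more dropout on KD and removes ketone-negative patients in that arm only. If leaving depends on observed scans and differs by arm, a likelihood-based analysis corrects for it and a completers-only analysis does not. If leaving depends on values never observed, neither is protected. The change should be made, but its absence would not by itself invalidate the trial.

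**What to change.** In section 10.b, replace the mixed ANOVA for Hypotheses 2–4 with a linear mixed model fitted by REML, and state:

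- **Fixed effects:** diet, session (1, 2, 3 as categories) and diet-by-session, with a named within-patient covariance.
- **Analysis set:** every randomised patient with at least one usable scan.
- **Deciding contrast:** diet-by-session, session 3 versus session 1. Add that session 1 (days 2–6) may fall after the diet starts, so the contrast measures change from an early scan that may be on diet.
- **Sensitivity analyses:** the completers-only ANOVA, and one that allows dropout not at random.

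The cost is SAP wording and some analysis set-up. The covariance structure and the voxel-level correction in 10.a must be specified for unbalanced data, which is simpler for region-of-interest outcomes than for whole-brain maps. No patient, scan or clinical procedure changes.
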